3. STUDY DESIGN

This is a 3-arm randomized clinical trial with a tai chi/qigong intervention, a 'sham' qigong control, and a standard of care wait list control condition. Both the intervention and control groups will be conducted online via Zoom videoconferencing (note: the in-person intervention was adapted to a virtual delivery due to Covid). The primary outcomes are the acceptability and the feasibility of the tai chi/qigong intervention for an older population living with HIV. The secondary outcomes are the reduction of psychological and physical symptoms. Participants ($n=48$) will be consented and baselined and randomized into either the qigong or the 'control' groups. The intervention duration is 12-weeks, 2x/week for the first 2 weeks, followed by 1 session per week. See below for a flowchart of the study design. Table 1 describes the tai chi/qigong intervention and the sham qigong control conditions.

Table 1. Descriptive characteristics of the TCQ Intervention and Control Conditions

	Qigong/Tai Chi Easy	Sham Qigong	Standard of Care
Intervention Features	Low impact physical activity Focus on breath Meditative State Incidental Social Support	Low impact physical activity with same/similar movements as TCQ intervention Incidental Social Support	No Exercise/Activity Program
Dose/Frequency	12-weeks, 1/week 60 min class (2x per week in first 2 weeks) Approx. 2 ½ hours home practice/week	12-weeks, 1/week 60 min class (2x per week in first 2 weeks) Approx. 2 ½ hours home practice/week	n/a
Controls for	Unique focus; breath and meditative state	Low impact physical activity	n/a

Figure 1. Flowchart depicting Study Design.

4. SELECTION AND ENROLLMENT OF PARTICIPANTS

4.1. Inclusion Criteria

- 50 years of age or older
- Must be HIV positive
- Able to provide consent
- Willing to participate the length of the study
- Have reliable internet access

4.2. Exclusion Criteria

- Regular involvement with mind-body interventions (yoga, tai chi, qigong) in the last 12 months (i.e., weekly practice for 3 months within the last 12 months)
- Not being able to stand for 10 minutes

4.3. Study Enrollment Procedures

Participants will be recruited either via Borinquen staff and recruitment flyers posted throughout the clinics as well as other partnering agencies and by using a professional recruiting service (Trialfacts) to conduct online recruiting.

Screening. Potential participants will be screened for eligibility using the IRB approved screener form and script (see Appendix). If potential participant is recruited via online, Trialfacts will provide the contact information and set up a time for research staff to call the participant. If determined eligible, the research interviewer will explain the study further and will fill out the Appointment and Scheduling Form. This form will be used to schedule the baseline assessment and will be placed in the participant study folder. Either the research coordinator or person screening will add the baseline appointment in the shared Qigong study google calendar. As part of the scheduling for baseline assessments, the interviewer will ask the participant to send a picture of their latest lab results for two reasons: 1) to confirm HIV status; and 2) to collect viral load data. The research coordinator should discuss with the PI when it was not possible to confirm HIV status. If found ineligible, the screener form will be kept in a separate folder, which will hold all ineligible screeners.

5. STUDY INTERVENTIONS

5.1. Interventions, Administration, and Duration

The Tai Chi/Qi gong Made Easy Intervention (TCQ). The TCQ intervention is standardized, manualized, and has a formal training program for instructors from the Institute of Integral Qigong and Tai Chi (IIQTC). We will follow a ‘train the trainers’ model, in which [name], who is an IIQTC Senior Trainer, will train 3-4 instructors on the intervention. The intervention content includes a series of repeated and easy to learn movements that are also the forms known to be linked to health benefits (Jahnke, et al., 2010). A DVD and manual demonstrating a core set of 10 exercises have been professionally produced and will be given to participants to help promote their practice at home. As part of the proposed study, we will translate and professionally produce a video (for home practice) in Spanish for Spanish speaking participants. This video will be in either a DVD format or streaming via YouTube.

The Sham Qigong is a physical activity- and attention-control group that uses similar types of movements that are part of the TCQ intervention, but without the meditative state and breath focus that is present in the TCQ group. It also has a video, participant manual, and instructor guidelines for teaching. [name] has been fully trained and experienced in this

protocol and will teach the research coordinator and 1-2 facilitators on how to use the video, manual, and practice. [name] will observe their practice via the video-recordings of the sessions and will oversee the respective fidelity checks. Both the TCQ intervention and the Sham qigong control group, will be revised based on the qualitative work done in the intervention refinement phase. [name] will review at least 10% of all sessions and hold monthly phone or video calls with trainers to review feedback.

Adherence/Incentive Strategies: Based on some of the elements of social cognitive theory (SCT), we will use role-modeling and social support, and intrinsic reward to help participants adhere to the intervention. These strategies are the following: 1) the instructor will communicate with each participant when they come to the session to reinforce self-efficacy; and 2) a monthly 1 page newsletter will be emailed to all participants (or handed out at classes) with success stories, participant adherence to intervention, and positive health outcomes of participants. In addition, the research coordinator will make 2 weekly phone calls as a reminder of upcoming sessions and to assess the participant's at-home practice. In addition, there will be monetary incentives for participating in each of the assessments and the intervention. We will provide a \$30 in cash for the baseline and 2 weeks follow up assessments each; and \$50 for the 3 months follow up assessment. If participants attend at least 75% of the sessions, the 2 weeks follow up assessment incentive will go up to a \$50.

5.2 Handling of Study Interventions

The TCQ intervention and SQG intervention has been used previously and is a standardized tai chi/qigong intervention including a manual of operations. This manual describes detailed instructions on how to deliver the TCQ and sham qigong intervention. The standard of care group will simply be no exercise or activity. Previous studies using the TCQ and sham qigong conditions show that *blinding* of the intervention was successful. Participants in both control conditions will be offered the TCQ class after their 3 months follow up assessment.

5.3 Concomitant Interventions

Not Applicable.

5.4 Adherence Assessment

Satisfaction surveys will be administered to each participant in the TCQ and in the SQG groups to assess adherence to the intervention (or control) group. Surveys will ask about their satisfaction with the groups, trainer, intervention content, home practice, video, the in-class 'buddy', and newsletter. Surveys will be administered before and after each session. The survey before each session will ask about the previous group they attended, and the survey administered after each session will assess satisfaction about that class.

Because acceptability and feasibility are the primary outcomes of the study, specific benchmarks were identified and approved by NCCIH to determine acceptability and feasibility. These are listed in the table below.

Table 2. Acceptability and Feasibility Benchmarks and Assessments

Aspects of Acceptability being Measured (adapted from Sekhon, et al (2017)[49])	Definition	Benchmark
Burden	Discontinuation/non-attendance	< 20% of TCQ and the sham qigong condition will drop out at 3 months follow up
Ethical Consequences	Any side effects with intervention	< 10% of participants will report any physical soreness or difficulties in doing qigong
Experience	Participant's experience and satisfaction	>80% qigong participants will perceive intervention positively >80% qigong participants will rate it very satisfactory or satisfactory
Affective Attitudes	Participants attitudes toward the intervention	>80% of participant in qigong condition will report positive attitudes about it (very good/good)
Opportunity Costs	Adherence and participation	Participants in both qigong and sham conditions will attend at least 75% of all sessions. Participants in the qigong condition will adhere to home practice at least 75% of the time expected (i.e., 112 out of 150 minutes/week)
Intentions	Willingness to participate	>80% qigong participants would be willing to participate again >80% qigong participants intend to continue qigong practice
Aspects of Feasibility being Measured (adapted from Bowen, et al., 2009 [50])	Definition	Benchmark
Demand	Likelihood that intervention will be used	>80% of qigong participants will report any qigong practice in the past week
Implementation	Can the intervention be implemented in a setting, often a real-world setting	Trainers will execute intervention >80% of the time >80% of trainers will rate resources needed to implement as very good/good

		>80% of trainers will report positive effects on population
Practicality	Extent to which an intervention can be delivered given the limited resources	>80% of trainers will report participant's ability to do the intervention as very good/good
Integration	Extent to which the intervention fits the system	>80% of trainers will perceive intervention fits the clinic infrastructure as very good/good >80% of trainers perceive the sustainability of the intervention as very good/good

6. STUDY PROCEDURES

Table 2. Measures and time of administration

Assessments	# of items/alpha	Screen	Baseline	Weekly/During Intervention	Post Intervention	3 month Follow up
Eligibility Age, HIV status (self-report/lab test) Any mind-body practice in past 12 months GAIN Cognitive Impairment Can stand up for 10 min	6-items	X X X X				
Demographics and Covariates^{85,86} HIV related stigma Social Support Scale DAST AUDIT	6-items/ $\alpha = .75$		X X		X X	X X
Psychological Symptoms^{87,88} Depression Anxiety & Stress Scale (DASS-21)	21 items/		X		X	X
Physical Symptoms^{89,90} The Revised Sign & Symptom Checklist for HIV (Holzemer) HIV-related Fatigue Scale (MAF)	45 items; $\alpha = .71 - .91$		X X		X X	X X
Adherence⁹¹ 5-item Adherence questions MMAS-8 Viral load (from participants)			X X		X X	X X
Feasibility # approached (if face-to-face) # screened # eligible # consented and enrolled		X X X X			X X X X	

# refused to participate Reasons for refusal # randomized into study % attended TCQ and control sessions % completed home practice % completed FU assessments		X X X			X X	X X	X
Acceptability Satisfaction surveys per session Satisfaction with adherence strategies (weekly calls, buddy system, etc)				X	X		
Feasibility of implementation in clinic setting (trainers)					X		
Intervention Fidelity Meditative Movement Inventory (participants) Intervention Fidelity Checklist	9 items; $\alpha = .86-.90$			X	X		

6.2 Description of Evaluations

6.2.1 Screening Evaluation and Process

These evaluations occur to determine if the candidate is eligible for the study.

Screening

A brief screening tool will be used to determine eligibility. It will include the following items:

- How old are you? (*must be 50 or over*)
- Are you HIV positive? (*must be positive*)
- Have you regularly participated (weekly for 3 months in the last 12 months) in any mind-body or alternative forms of exercise such as yoga, tai chi, qigong, or meditation in the last 12 months? (*must answer no*)
- They must pass the GAIN Cognitive Impairment Scale (based on scoring instructions) to determine if they are able to go through the consenting process and trial
- Can you stand for more than 10 minutes at a time? (answer must be yes)
- Do you have reliable internet access?

Research staff will be screening persons over the phone. During the screening process, all persons screened will not provide their names. They will be given a screening ID number and, if found eligible, the interviewer will ask for a first name only, phone number, and will schedule the person for a baseline assessment during which they will be consented and enrolled into the study. People screened and found eligible will be scheduled for a baseline assessment within 2 weeks of the screening. Appointments will be entered into the study google calendar. No names will be used to set the appointments in the calendar. Only screening ID numbers will be used to hold appointment times. If found ineligible, their screener form will be kept in a folder in a locked filing cabinet (see Appendix for the Screener form and script).

6.2.2 Enrollment, Baseline, and/or Randomization

Enrollment

The enrollment date is the date of the baseline assessment. At this assessment, the participant will be consented, complete all baseline assessments, and then randomized into one of three conditions. Assessments will be administered using RedCAP.

Baseline Assessment

Research staff will call all participants scheduled for a baseline assessment the day before the assessment to confirm attendance. All assessments are done via phone due to Covid restrictions. Assessors should have:

- Participant study folder labeled with assigned PID number
- Baseline checklist
- Informed Consent Form
- Monetary incentive with log form (if paying participants at the time of interview)
- List of computer-generated randomized group assignments (Only Research coordinator will provide to assessors)

The participant study folder should also include the adverse event form, follow up visit checklist, and study completion forms for future use as applicable.

Consenting Procedure. The baseline assessment begins with the consenting process. The research interviewer will be well-trained on the consenting process as well as the baseline measures. The interviewer will provide the participant with the informed consent form to read, but the interviewer will also explain the purpose of the study and will summarize the main points (e.g., procedures to expect; confidentiality will be maintained; they can stop participation at any time; participation will not affect treatment at Borinquen or Pridelines (if recruited from clinics); incentives will be provided, and any risks and benefits to participation). Consent forms will be available in English or Spanish. The Spanish consent forms will be back translated. At the end of the consenting process, the interviewers will ask participants if they have any questions. All consents will be verbal consent and done via the phone. Forms must be signed by the interviewer (as a witness) and will be stored separate from any other data or identifying information in a locked file cabinet in the FIU midtown research office which is locked nightly.

Once the participant signs the consent form, the research assistant sends participant a Qualtrics link to attach a photo of their most recent lab report or medication bottle (this is to confirm status), completes the locator form with the participant, and then begins the interviewer-administered RedCAP survey. The photos will be stored in Qualtrics secure server.

The Locator Form is used to help remind participants about upcoming groups, to assess acceptability via phone calls, and schedule participants for their follow up appointments. The locator form will be part of the baseline assessment and administered using RedCAP.

Baseline Measures. The following are all the baseline measures by domains that will be administered via RedCAP (see the Appendix for detailed scale items):

- Demographics
- Covariates (HIV stigma, social support, alcohol use, drug use)
- Psychological symptoms (depression, anxiety, general distress)
- Physical symptoms (HIV symptoms scale, HIV fatigue scale)

Randomization

Once the baseline assessment is complete, each participant will be assigned by the research coordinator to one of three conditions. A randomization scheme will be developed in SAS, generating group assignments. Randomized group assignments will then be in the format of a list kept by the research coordinator. After each baseline assessment, the research coordinator will look at the randomization list and assign the participant to the next group assignment on the list. Only the research coordinator will know the group assignment. Randomization will be tested after baseline assessments are all complete by comparing demographics across conditions.

6.2.3 Blinding

The participants will be blind to their condition, except for the group that receives the standard of care (which is no group). The study will be promoted as a “Gentle Empowering Movement” program about wellness, or The G.E.M. Study. Those in the sham qigong intervention will not be able to tell if they are in the intervention or in the control group. The research interviewer will also be blind to group assignment.

6.2.4 Follow-up Visits

There will be 2 follow-up visits: at 2 weeks post intervention and at 3-month post intervention. One week after a cohort has ended, research staff will begin to schedule the 2 week FU assessments. These assessments are on RedCAP and will also include some acceptability measures. Interviewers should begin the 2 week follow up by going over the locator form and confirm if information is still accurate. Then, interviewer should administer the RedCAP survey via phone. At the end of the interview, each participant will set up a time to come to the office to pick up their incentive (NOTE: Prior to the 2 week follow up assessments, the research coordinator confirms whether participant attended more than 75% of the group sessions or not in order to determine the incentive level).

For the **2-week post intervention**, the following will be assessed:

- Covariates (HIV stigma, social support, alcohol use, drug use)
- Psychological symptoms (depression, anxiety, general distress)
- Physical symptoms (HIV symptoms scale, HIV fatigue scale)
- Acceptability Measures
- Feasibility Measures

6.2.5 Completion/Final Evaluation

- For the **3 months follow up** assessment:
- Covariates (HIV stigma, social support, alcohol use, drug use)
- Psychological symptoms (depression, anxiety, general distress)
- Physical symptoms (HIV symptoms scale, HIV fatigue scale)
- Acceptability Measures
- Feasibility Measures

At the 3 month follow up, interviewers will administer the survey questions on RedCAP. Once the appropriate level of incentives is provided to participant, the interviewer will complete the Study Completion Form. This form will be placed in the participant study folder. If the participant completing the study is from either of the control conditions, they will be offered the TCQ intervention.

Weekly assessments

In addition, acceptability and feasibility will be assessed every week either in person regarding each session or via the weekly calls. Weekly calls will ask about adherence to home practice; and acceptability of home practice, and satisfaction with the intervention. A brief satisfaction survey will be administered to each participant after each group session.

7. SAFETY ASSESSMENTS

7.1 Specification of Safety Parameters

See below

7.2 Methods and Timing for Assessing, Recording, and Analyzing Safety Parameters

All safety parameters will be assessed, recorded, and analyzed by the research team through weekly meetings between the PI and staff; monthly investigator meetings; and the DSMB meetings every 6 months. Safety issues will be part of every DSMB agenda. There will be a protocol in place for addressing safety issues (See DSMB Plan).

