7.3 Adverse Events and Serious Adverse Events

Serious Adverse Events (SAE): An experience occurring during study participation that may involve imminent danger to the participant or others. For this study, SAEs include the following events that occur after entrance into the study:

- Death, serious injury, a life-threatening experience, drug overdose, or suicide attempt
- Hospitalization or prolongation of hospitalization (including medical or psychiatric hospitalization)
- Persistent or significant disability or incapacity
- An unanticipated event that, in the PI's judgement, represents a significant hazard or potentially serious harm to research participants or others.

Adverse Events (AE): An untoward experience occurring during study participation that does not rise to the level of an SAE. For this study, specific AEs include the following events that occur after entrance into the study:

- Increased substance use, medical problems, emotional problems, or victimization

- Significant physical or emotional pain, homicidal thoughts, or suicidal thoughts
- Breach of confidentiality
- An unanticipated event that, in the PI's judgement, represents a non-serious adverse event that nonetheless resulted in increased risk to research participants or others

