7.5 Follow-up for Adverse Events and Safety Monitoring

All research and intervention staff will be trained on the definitions of SAEs and AEs and its reporting procedures. Staff will notify the PI immediately after the occurrence of an SAE or AE. Weekly meetings between staff and investigators will have SAEs and AEs as an agenda item. All SAEs and AEs will be reviewed by the PI for severity and whether it is attributed to the intervention. SAEs will be reported to NCCIH and to the FIU IRB within 24 hours, with a written report within 48 hours. For all SAE's, the Event Report Form will be completed by the PI. The research coordinator will keep a log of all adverse events, unanticipated problems, and protocol deviations on the Adverse Event Log Form. All AEs that occur during the study will be documented and reported by the investigators to NCCIH and the FIU IRB at the time of their continuing annual reviews. Participants that suffer an SAE or AE due to the study and still want to continue participating in the study, may do so if the PI agrees that continued participation is safe.

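### No scheduled assessment is specified as asking about adverse events or soreness, so capture of harms is passive and contact-dependent, and the <10% soreness benchmark can be met through non-report

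*Combined protocol and SAP*

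**What the plan says.** **Safety sections.** Sections 7.1 and 7.4 only point onward. Section 7.2, on methods and timing, says "All safety parameters will be assessed, recorded, and analyzed by the research team through weekly meetings between the PI and staff", and adds monthly investigator meetings and six-monthly DSMB meetings. Section 7.3 defines serious events, including hospitalisation and serious injury, and adverse events, including "Increased substance use, medical problems, emotional problems, or victimization". Section 7.5 begins at the point where an event is already known: "Staff will notify the PI immediately after the occurrence of an SAE or AE". Section 6.2.2 places an adverse event form in each participant folder for use as applicable, and Section 7.5 requires an adverse event log.

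**Schedule.** The table in Section 6 headed "Table 2. Measures and time of administration" has no row for adverse events, injury or soreness. The 2-week list (6.2.4) and the 3-month list (6.2.5) name covariates, psychological symptoms, physical symptoms, and acceptability and feasibility measures.

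**Class-arm contacts.** For the session surveys, Section 5.4 says: "Surveys will ask about their satisfaction with the groups, trainer, intervention content, home practice, video", followed by the buddy and the newsletter. For the calls, Section 6.2.5 says: "Weekly calls will ask about adherence to home practice", plus acceptability and satisfaction.

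**Benchmark.** The benchmark table in Section 5.4 (also numbered Table 2) lists an aspect of acceptability defined as "Any side effects with intervention", with the target "< 10% of participants will report any physical soreness or difficulties in doing qigong".

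**The concern.** Nothing in the text says how staff learn of an event. If participants are not asked, capture depends on what they volunteer and how often they speak to staff. Three things rest on it.

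- **Oversight.** Section 8 provides for stopping the study if a review of adverse events shows significant harms, and Section 12 has the DSMB judge continuation. Both reviews are only as complete as the events that reach them.
- **Comparison across arms.** The class arms meet staff every week and the wait-list arm does not. With volunteered reports, more contact means more chances to report.
- **A primary outcome.** Acceptability is primary, and side effects are one of its benchmarked aspects. The target counts those who report soreness. A participant who was never asked, or did not answer, is indistinguishable from one who had none.

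**Working it through.** **1. Is a question specified anywhere?** Setting the places side by side:

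- 7.2: meetings only.
- 7.5: starts from a known event.
- Section 6 measures table: no adverse-event or soreness row.
- 6.2.4 and 6.2.5 visit lists: no adverse-event item; the acceptability measures are not itemised.
- 5.4 session surveys: satisfaction topics.
- 6.2.5 weekly calls: home practice, acceptability and satisfaction.
- 6.2.2 adverse event form: no visit is said to complete it.

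The alcohol, drug, DASS-21, HIV symptom and fatigue scales are given at baseline and both follow-ups with no arm excluded. They overlap some categories in 7.3, but no rule turns a score into a recorded event, and none is described as covering hospitalisation, injury or victimisation.

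**2. Scheduled contacts between baseline and the post-intervention interview**

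- Classes (Section 3): 2 × 2 + 10 × 1 = 14.
- Calls: 2 × 12 = 24 if Section 5.1 means two a week; 12 if one a week.
- TCQ and sham: 14 + 12 = 26 to 14 + 24 = 38 per participant.
- Wait-list: 0 individual contacts. The monthly newsletter goes to all participants but asks nothing.

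That calls go only to the class arms is an inference from their stated purpose: session reminders and home practice.

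**3. What non-report does to the soreness benchmark**

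The 10% threshold has no derivation, so there is no plan figure to reproduce. Inputs:

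- Arm size n = 48/3 = 16. This is an assumption: Section 9.1 states 24 per arm, which would need 3 × 24 = 72.
- Passing means at most 1 of 16, since 1/16 = 6.3% and 2/16 = 12.5%.
- True soreness rate r and share reported s are not in the documents. Both are assumed and shown over a range.

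With q = r × s, P(pass) = (1 − q)^16 + 16q(1 − q)^15.

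At r = 20%:

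- s = 100%, q = 0.20: 0.0281 + 0.1126 = 0.141
- s = 50%, q = 0.10: 0.1853 + 0.3294 = 0.515 (0.5147 before rounding)
- s = 25%, q = 0.05: 0.4401 + 0.3706 = 0.811

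| True rate | All reported | Half | Quarter | None |
|---|---|---|---|---|
| 10% | 0.515 | 0.811 | 0.941 | 1.000 |
| 20% | 0.141 | 0.515 | 0.811 | 1.000 |
| 30% | 0.026 | 0.284 | 0.660 | 1.000 |
| 40% | 0.003 | 0.141 | 0.515 | 1.000 |

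**Sensitivity to arm size, at r = 20%.** With n = 24 (at most 2 cases) the three values are 0.115, 0.564 and 0.884. With n = 32, TCQ plus sham (at most 3), they are 0.093, 0.600 and 0.926.

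**Sensitivity to the denominator, full reporting.** If TCQ cases are counted over all 48, a pass allows 4 (4/48 = 8.3%), and P(pass) is 0.798 instead of 0.141.

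**Precision.** By Wilson's method, which Section 9.1 names, 1/16 has a 95% interval of 1.1% to 28.3%. Zero of 16 still has an upper limit of 19.4%.

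**The case against.** A reader might infer that participants are never asked about harms. The documents do not support that. Item wording is in an Appendix, and safety handling is partly deferred to a DSMB Plan; neither is available. Side effects are classed as an aspect of acceptability, and unspecified acceptability measures are scheduled weekly and at both follow-ups, so a soreness item may exist. Section 9.1 also counts whether participants can do the movements as feasibility. Increased substance use is partly covered by the repeated alcohol and drug measures, and staff are trained on the event definitions. All of this stands: the supportable statement is that no question is specified.

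A reader might also infer that harms are under-counted unequally by arm. That is not shown. Contact counts measure opportunity to report, not reports. Section 9.1 plans mainly descriptive analysis and states no between-arm adverse-event comparison. TCQ and sham share one contact schedule, so that contrast is less exposed. The wait-list gap has no bearing on a soreness benchmark restricted to class participants.

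Finally, the reporting shares and true rates are assumed, and the benchmark is weak at this size in any case: at a true rate of 10% with full reporting it is passed 51% of the time. That stands too, but it does not explain the rise down to quarter reporting, which occurs at every true rate shown.

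**Conclusion.** The point holds in a limited form. The text specifies no question about adverse events or soreness at any scheduled assessment. Followed as written, capture of hospitalisation, injury and victimisation is passive, with 26 to 38 scheduled contacts per class participant against none in the wait-list arm over the intervention period. A class-versus-wait-list tabulation of harms would carry a risk of distortion; actual under-counting is not established.

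Separately, the soreness benchmark lacks an item, a time point and a denominator, and its wording lets non-report count in its favour. At an assumed 20% true rate and 16 TCQ participants, the chance of passing goes from 14% with full reporting to 51% with half and 81% with a quarter. The sizes depend on those assumptions; the direction does not. This should be corrected. If suitable items already exist in the Appendix, citing them in the schedule with their time points would answer much of the concern.

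**What to change.** 1. Add one fixed adverse-event question set (hospitalisation, injury, new or worse physical or emotional problem since the last interview) to the existing 2-week and 3-month interviews, worded identically in all three arms. Add the row to the measures table.
2. Base any between-arm harms table on those two points. Report events learned at classes or on calls separately.
3. Name one soreness or difficulty item as the benchmark's source, with its time point and with TCQ participants who answered as the denominator. State that an unanswered item does not count as no soreness, and report how many did not answer.
4. Reconcile the 48 total with the 24 per arm in Section 9.1, since the number of cases allowed depends on it.

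**Cost.** A few REDCap items in interviews already scheduled, one schedule row, and a short text change. Because NCCIH approved the benchmarks, the sponsor should confirm the clarified measure with it. Reported event rates will rise, and the soreness benchmark will be harder to meet.
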